7.1.2. Discontinuation Procedures

In the event that the decision is made to permanently discontinue the study treatment, the EOT visit should be conducted. Reasonable efforts should be made to have the participant return for a follow-up visit. These visits are described in [Table 3](#) and [Table 4](#). The last date of the last dose of study drug and the reason for discontinuation of study treatment will be recorded in the eCRF.

If a participant is discontinued from study treatment:

- The study monitor or sponsor must be notified.
- The reason(s) for discontinuation must be documented in the participant's medical record and the primary reason for withdrawal must be included in the eCRF.
- The EOT visit should be performed and date recorded.
- The status of the participant should be updated to EOT in the IWRS.
- Participants must be followed for safety until the time of the follow-up visit or until study drug-related toxicities resolve, return to baseline, or are deemed irreversible, whichever is longest.

If the participant discontinues study treatment and actively withdraws consent for collection of follow-up data (safety follow-up or disease assessment), then no additional data collection should occur; however, participants will have the option of withdrawing consent for study treatment but continuing in the follow-up period of the study for safety/efficacy and survival per the schedule of assessments.

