8.8. Follow-Up

8.8.1. Safety Follow-Up

The safety follow-up period is the interval between the EOT visit and the scheduled follow-up visit, which should occur 30 to 35 days after the EOT visit (or after the last dose of study drug/treatment if the EOT visit was not performed). Adverse events and SAEs must be reported up until 1) at least 30 days after the last dose of study drug or the start of a new anti-lymphoma therapy or 2) until toxicities resolve, return to baseline, or are deemed irreversible. Reasonable efforts should be made to have the participant return for the follow-up visit and report any AEs that may occur during this period.

If a participant is scheduled to begin a new anti-lymphoma therapy before the end of the safety follow-up period, the safety follow-up visit should be performed before a new anti-lymphoma therapy is started. Once a new anti-lymphoma therapy has been initiated, the participant will move into the survival follow-up period.

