- Once an AE is detected, it should be followed until the end of safety follow-up periods. All SAEs and nonserious AESIs should be followed until resolution, stabilization, the event is otherwise explained, or the participant is lost to follow-up. Assessment should be made at each visit (or more frequently if necessary) of any changes in severity, the suspected relationship to the study drug, the interventions required to treat the event, and the outcome.
- When the severity of an AE changes over time for a reporting period (eg, between visits), each change in severity will be reported as a separate AE.
- Updated SAE information will be recorded in the originally completed eCRF and reported to Incyte Pharmacovigilance until resolution, stabilization, the event is otherwise explained, or the participant is lost to follow-up.
- Any updated SAE data (including SAEs being downgraded to nonserious) will be submitted to the sponsor (or designee) within 24 hours of receipt of the information.

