9.4. Reporting of Serious Adverse Events

Regardless of suspected causality (eg, relationship to study drugs, reference therapy, or study procedure), all SAEs occurring after the participant has signed the ICF through the last safety study visit, or until the participant starts a new anticancer therapy must be reported to the sponsor (or designee) immediately, without undue delay but not later than within **24 hours** of obtaining knowledge of its occurrence unless otherwise specified by the Protocol. The investigator will submit any updated SAE data to the sponsor (or designee) within 24 hours of it being available. This information must also be reported immediately to the head of the study site.

Investigators are not obligated to actively seek SAE information after the safety follow-up visit or 30 to 35 days after the last dose of study treatment. If the investigator learns of any SAE, including death, at any time during this period, and they consider the event to be reasonably related to the study treatment or study participation, then the investigator must notify the sponsor (or designee) within 24 hours of becoming aware of the event.

After the initial AE/SAE report, the investigator is required to proactively follow each participant at subsequent visits/contacts. All SAEs and AEs of special interest (as defined in Section 9.5.1) will be followed until resolution, stabilization, the event is otherwise explained, or the participant is lost to follow-up (as defined in Section 7.3).

Prompt notification by the investigator to the sponsor of an SAE is essential so that legal obligations and ethical responsibilities towards the safety of participants and the safety of a study treatment under clinical investigation are met.

If the SAE is not documented in the RSI of the [parsaclisib IB](#) for the study treatment (new occurrence) and is thought to be related to the sponsor's study treatment, the sponsor or its designee may urgently require further information from the investigator for expedited reporting to health authorities. The sponsor or its designee may need to issue an Investigator Notification to inform all investigators involved in any study with the same drug that this SAE has been reported. The sponsor will report suspected expected deaths and life-threatening events to the PMDA as per local regulatory requirements.

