#### 4.1.4. Handling of Missing and Incomplete Data

In general, values for missing data will not be imputed unless methods for handling missing data are specified in this section or relevant sections. The original reported dates collected on the eCRF should be used in all relevant listings. The following rules will be used for handling missing or partial dates for analyses requiring dates.

When calculating time since initial diagnosis of cancer, partial diagnosis date will be handled in the calculation as follows:

- If only the day is missing, then the first day of the month will be used.
- If both the month and day are missing, then 01 JAN will be used.
- Otherwise, the time since diagnosis will not be calculated.

When the date of the last dose is used in deriving variables such as duration of treatment or TEAE flag, missing or partial date of last dose will be handled in the calculation as follows:

- If only the day is missing, then the earlier date of the last day of the month or the date that the participant discontinued treatment will be used.
- If both the month and day are missing, then the earlier date of 31 DEC of the year or the date that the participant discontinued treatment will be used.
- Otherwise, the date that the participant discontinued treatment will be used as the date of the last dose.

When calculating DOR, PFS, and OS, a partial date of death will be handled in the calculation as follows:

- If mmyyyy for the last known alive date = mmyyyy for the death date, then the day after the last known alive date will be used.
- If mmyyyy for the last known alive date < mmyyyy for the death date, then the first day of the death month will be used.
- Otherwise, the partial death date will not be handled.

When calculating time to onset or duration of a TEAE, a partial or missing AE onset/end date will be handled in the calculation as follows:

- If only the day is missing, then the first day of the month or Day 1, whichever is later, will be used as the onset date; the earlier date of the last day of the month or the date that the participant discontinued study or died will be used as the end date.
- If both the month and day are missing, then 01 JAN or Day 1, whichever is later, will be used as the onset date; the earlier date of 31 DEC or the date that the participant discontinued study or died will be used as the end date.
- Otherwise, Day 1 will be used as the onset date, and the missing end date will not be handled.

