The longest duration of a TEAE of any grade is defined as the longest interval between the date of occurrence of a TEAE and the date of resolution. The longest duration of a Grade 3 or higher TEAE is defined as the longest interval between the date of occurrence of a Grade 3 or higher TEAE and the date of improvement to Grade 2 or lower. If participants have missing or partial onset/end date of a TEAE, the partial or missing dates will be handled using the rules explained in Section 4.1.4. Participants who have missing end date of a TEAE at the time of analysis will be right-censored using the following algorithm:

- If the TEAE is serious, then the participant will be censored at the earlier date of data cutoff, study discontinuation, and death.
- If the TEAE is not serious,
  - If the participant is ongoing with study treatment, then the participant will be censored at the data cutoff date, OR
  - If the participant discontinued treatment, then the participant will be censored at date of safety follow-up visit, or 35 days after the end of treatment visit (or after the last dose if the end of treatment visit was not performed), whichever is later; the censored date will be truncated by the earlier date of data cutoff, study discontinuation, and death if beyond.

Longest duration of new or worsening Grade 3 or higher colitis, diarrhea, rash, and febrile neutropenia will be summarized. In addition, longest duration of new or worsening AEs of any grade will be summarized for colitis, diarrhea, and rash.

The total number of participants whose TEAE of any grade resolved or whose Grade 3 or higher TEAE improved to Grade 2 or lower and the number of participants censored will be summarized. The Kaplan-Meier estimate of median time to resolution/improvement and its 95% CIs will be provided, with the CIs calculated using the generalization of Brookmeyer and Crowley's method (1982) with log-log transformation (Klein and Moeschberger 1997). Resolution/improvement rates at selected timepoints will also be provided with 95% CIs calculated using Greenwood's formula to estimate the standard error.

TEAEs of special interest to be summarized may be adjusted based on emerging data.

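### SAP 9.2.2 sets a censoring limit for open nonserious off-treatment events but none for recorded end dates, so late resolution rates are biased upward if late end dates are entered

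*SAP*

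**What the plan says.** SAP 9.2.2 plans Kaplan-Meier medians and timepoint rates for time to resolution (any-grade colitis, diarrhea and rash) and for time to improvement to Grade 2 or lower (Grade 3 or higher colitis, diarrhea, rash and febrile neutropenia).

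The censoring algorithm is confined to open events: "Participants who have missing end date of a TEAE at the time of analysis will be right-censored using the following algorithm". It has three branches:

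- Serious: "If the TEAE is serious, then the participant will be censored at the earlier date of data cutoff, study discontinuation, and death".
- Nonserious, still on treatment: censored at data cutoff.
- Nonserious, off treatment: "then the participant will be censored at date of safety follow-up visit, or 35 days after the end of treatment visit", whichever is later. This censoring date is shortened if cutoff, study discontinuation or death comes first.

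Nothing in the section limits a recorded end date. SAP 4.1.4 does not supply a limit either. When only the day is missing, the end date becomes "the earlier date of the last day of the month or the date that the participant discontinued study or died", with no reference to the safety visit.

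On follow-up, Protocol 9.3 treats serious events and nonserious events of special interest alike: "All SAEs and nonserious AESIs should be followed until resolution, stabilization, the event is otherwise explained, or the participant is lost to follow-up". Protocol 9.4 repeats this ("All SAEs and AEs of special interest (as defined in Section 9.5.1) will be followed until resolution, stabilization"), and Protocol 8.3.1 has the same rule. Protocol 7.1.2 extends safety follow-up after discontinuation "until study drug-related toxicities resolve, return to baseline, or are deemed irreversible, whichever is longest".

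**The concern.** Take two nonserious rashes, both open at the limit in participants off treatment. One resolves a month later and its end date is entered. The other never resolves. Under SAP 9.2.2 the first stays at risk and counts as a resolution on its own date, while the second leaves the risk set at the limit. Whether an event is censored at the limit then depends on what happens to it afterwards, so the censoring is informative. It removes only non-resolvers, so the estimated resolution rate after the limit can only move up.

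At stake is how reversible these toxicities appear after the drug is stopped. Colitis, diarrhea of Grade 2 or higher and rash of Grade 2 or higher are on the Protocol's list of events of special interest (Protocol 9.5.1). The affected outputs are SAP Table 3.2.29 and Figure 4.5.2. The primary endpoint is not touched.

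**Working it through.** The documents give no figure for time to resolution, so there is nothing of the plan's own to reproduce. The check asks how far the rule can move a late rate.

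**Inputs from the documents.** 40 participants (Protocol 10.1) and 31% rash of any grade in Study INCB 50465-101 (Protocol 2.1.3): 0.31 × 40 = 12.4, about 12 participants with rash.

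**Assumptions, not in the documents.** Of the 12 events:

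- k are nonserious, off treatment and open at the limit.
- r of those k resolve later and have the end date entered.
- m others (serious or on treatment) stay at risk past the last late resolution.
- The remaining 12 − k − m resolved earlier.

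One common limit is used for simplicity. In the trial it runs from each participant's end of treatment, so it varies in time since onset.

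**Formulas** (S = proportion unresolved):

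1. At the limit: S = (k + m)/12.
2. After the last late resolution, SAP rule: k − r are censored at the limit and r of the remaining r + m resolve, so S = (k + m)/12 × m/(r + m).
3. If the k − r open events were instead followed past that time: S = (k + m − r)/12.
4. Overstatement of the resolution rate = (3) − (2) = r(k − r) / [12(r + m)].

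The overstatement is never negative, and it is zero if r = 0 or r = k.

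Example, k = 2, r = 1, m = 1: (2) gives 3/12 × 1/2 = 0.125, or 87.5% resolved. (3) gives 2/12 = 0.167, or 83.3%. The difference is 4.2 points.

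For k = 2 to 4 and 0 < r < k:

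| m | Smallest (k = 2, r = 1) | Largest (k = 4) |
|---|---|---|
| 0 | 1/12 = 8.3 points | 3/12 = 25.0 (r = 1) |
| 1 | 1/24 = 4.2 | 3/24 = 12.5 (r = 1) |
| 2 | 1/36 = 2.8 | 4/48 = 8.3 (r = 2) |
| 4 | 1/60 = 1.7 | 4/72 = 5.6 (r = 2) |
| 6 | 1/84 = 1.2 | 4/96 = 4.2 (r = 2) |

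**Large-sample check by simulation.** Assumed: exponential time to resolution among resolvers, end of treatment 0 to 30 days after onset (so the limit falls 35 to 65 days after onset), and cutoff 90 to 400 days after onset. Resolution rates at 90/180 days, in percent:

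| Scenario | True | SAP rule | Difference |
|---|---|---|---|
| Median 30 d, 20% never resolve, 60% off treatment, no late dates entered | 70.0/78.8 | 70.1/78.9 | about 0 |
| Median 30 d, all resolve, 60% off, all late dates entered | 87.5/98.4 | 88.2/98.9 | +0.7/+0.5 |
| Median 30 d, 20% never, 60% off, all entered | 70.0/78.8 | 75.7/87.8 | +5.7/+9.0 |
| Median 30 d, 20% never, all off, all entered | 70.0/78.8 | 83.0/98.6 | +13.0/+19.8 |
| Median 60 d, 20% never, all off, all entered | 51.7/70.0 | 63.4/91.9 | +11.7/+21.9 |

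Rates at 30 days, before any limit, match the truth in every scenario. In the last row the estimated median also falls, from about 85 to about 70 days, because it lies beyond the limit.

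**Same limit applied to every event.** In the third scenario the rates become 69.9/78.6, so the bias is gone. With everyone off treatment nothing is observed beyond day 65, and the late rates cannot be estimated.

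**The case against.** The strongest reply is that late end dates may never be entered. In Protocol 9.3 the end-date item makes an exception for events still unresolved at the final safety visit, and the same section has AEs in general followed only to the end of safety follow-up. Protocol Table 3 schedules no AE assessment after that visit. The SAP's 35 days also matches the end of the visit window, so the rule may simply mark the last date on which status is collected. If so, both kinds of event are censored at the limit and nothing is wrong.

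This stands to the extent that the premise is conditional. It does not settle the matter. Protocol 8.8.1 has AEs reported for the visit window or "until toxicities resolve, return to baseline, or are deemed irreversible". The end-date item in Protocol 9.3 also covers serious events, whose later updates clearly are recorded in the eCRF, so it is not a general bar on later dates.

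The second reply is that few events qualify. They must be nonserious, off treatment and open beyond the limit. Grade 1 diarrhea, Grade 1 rash and febrile neutropenia are not on the Protocol 9.5.1 list, so they get extended follow-up only if drug-related. The timepoints for the rates are unspecified and may precede the limit. All of this stands and keeps the point small.

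A reader might infer from the top of the range that these rates will be overstated by 20 points or more. The documents do not support that. They give no counts for k, r or m, the base of 12 counts rash of any grade, and the 25-point case has a single participant left at risk, so the curve jumps to 100%. Nor do they show that the safety visit is a wrong censoring date in itself. For an event already stable or irreversible by then, the Protocol may require nothing further, and the visit is then the right date.

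**Conclusion.** The asymmetry is in the text: open nonserious off-treatment events have a limit and recorded end dates do not. Whether it causes bias depends on whether end dates after the limit are entered, which the Protocol leaves unsettled. If they are, Kaplan-Meier resolution and improvement rates after the limit are biased upward. Rates before it are not, and the median moves only if it falls after it.

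The size is unknown. It is zero if no late dates are entered, or if none or all of the open events resolve late. It is under 1 to 2 points in mild cases where many events stay at risk, intermediate otherwise, and about 20 points or more only when almost nothing else stays at risk. All nonzero figures rest on assumed counts and distributions.

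This is a cheap improvement to a secondary descriptive safety summary, worth making but not essential.

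**What to change.** Add one sentence to the nonserious, off-treatment branch of SAP 9.2.2, along these lines:

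> For a nonserious TEAE in a participant who has discontinued treatment, a resolution or improvement date later than the limit above, after any partial-date handling under Section 4.1.4, is censored at that limit.

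This changes nothing if no late dates are entered and removes the bias if they are. It needs no new data and no change to the eCRF, only one derivation used in Table 3.2.29 and Figure 4.5.2.

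The cost is that genuine late resolutions drop out of the Kaplan-Meier analysis, and late rates may not be estimable if few events stay at risk. The late end dates can still be shown in the AE listing (Listing 2.7.1).

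The alternative is to censor open events at the date they were last known to be ongoing. That would keep the late data, but the date is not among the AE items in Protocol 9.3. For events whose follow-up stops at stabilization it could fall at the safety visit and bring the same asymmetry back.

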### 9.2.3. Adverse Event Summaries

Overall summaries of TEAEs will be provided during the parsaclisib initial QD dosing period, maintenance dosing period, and overall period (ie, all TEAEs regardless of the timing of occurrence). These summaries will include the following:

- Number (%) of participants reporting any TEAEs
- Number (%) of participants reporting any Grade 3 or higher TEAEs
- Number (%) of participants reporting any serious TEAEs
- Number (%) of participants reporting any TEAEs related to parsaclisib
- Number (%) of participants reporting any Grade 3 or higher TEAEs related to parsaclisib
- Number (%) of participants reporting any serious TEAEs related to parsaclisib
- Number (%) of participants who had TEAE with fatal outcome
- Number (%) of participants with parsaclisib dose reductions because of TEAEs
- Number (%) of participants who temporarily interrupted parsaclisib because of TEAEs
- Number (%) of participants who permanently discontinued parsaclisib because of TEAEs

The following summaries will be produced for TEAEs during the overall period by MedDRA term (if 5 or fewer participants appear in a table, a listing may be appropriate):

- Summary of TEAEs by SOC and PT
- Summary of TEAEs by PT in decreasing order of frequency
- Summary of TEAEs by SOC, PT, and maximum severity
- Summary of TEAEs by PT and maximum severity in decreasing order of frequency
- Summary of Grade 3 or higher TEAEs by SOC and PT
- Summary of Grade 3 or higher TEAEs by PT in decreasing order of frequency

- Summary of serious TEAEs by SOC and PT
- Summary of serious TEAEs by PT in decreasing order of frequency
- Summary of parsaclisib treatment-related TEAEs by SOC and PT
- Summary of parsaclisib treatment-related TEAEs by PT in decreasing order of frequency
- Summary of parsaclisib treatment-related TEAEs by SOC, PT, and maximum severity
- Summary of Grade 3 or higher parsaclisib treatment-related TEAEs by SOC and PT
- Summary of parsaclisib treatment-related serious TEAEs by SOC and PT
- Summary of TEAEs with a fatal outcome by SOC and PT
- Summary of TEAEs leading to parsaclisib dose reduction by SOC and PT
- Summary of TEAEs leading to parsaclisib dose interruption by SOC and PT
- Summary of TEAEs leading to discontinuation of parsaclisib by SOC and PT
- Summary of selected TEAEs of special interest by maximum severity
- Summary of time to onset of selected TEAEs of special interest
- Summary of time to onset of selected TEAEs of special interest: life-table method
- Summary of longest duration of selected TEAEs of special interest

The following supporting summaries will be produced for TEAEs during the parsaclisib initial QD dosing period and the maintenance dosing period by MedDRA term.

- Summary of TEAEs by PT in decreasing order of frequency
- Summary of TEAEs by PT and maximum severity in decreasing order of frequency
- Summary of Grade 3 or higher TEAEs by PT in decreasing order of frequency
- Summary of serious TEAEs by PT in decreasing order of frequency
- Summary of TEAEs with a fatal outcome by SOC and PT
- Summary of TEAEs leading to discontinuation of parsaclisib by SOC and PT

## **9.3. Clinical Laboratory Tests**

### **9.3.1. Laboratory Value Definitions**

Laboratory values and change from baseline values will be summarized descriptively by visit. Baseline will be determined according to Section 4.1.3. If there are multiple values that meet the criteria for baseline, the value from the central laboratory has priority over the value from the local laboratory. Thereafter, additional rules may be provided after consultation with the medical monitor to delineate which value will be defined as baseline.

Laboratory test values will be assessed for severity based on the numerical component of CTCAE v5.0.

